- Taking part in more than one research study may be harmful to the subject. If subjects are already taking part in another study, we ask that they let us know. Subjects should not take part in more than one study at the same time, unless the subject and the investigators agree that the subject is not likely to be harmed, and the outcome of the study will not be disturbed. RARE
- As with any research study, though, there may be additional risks of participating that are unforeseeable or hard to predict. RARE

What will be done to reduce or monitor these risks?

- Any information sharing would only be done in the context of a new IRB review and in concert with UM's Data Management Office. To minimize the breach of confidentiality risk, information shared outside of the University of Michigan will not use the subject's name or hospital number, but rather a unique study number, and would only occur under a data use agreement supported by the University. Any publications that result from this work will only report de-identified data.
- The site investigators for this trial are allergists. They are trained to recognize symptoms and are expert in the treatment of anaphylaxis. They will be available within 60 seconds in the event of a reaction. Emergency medications, oxygen, and equipment will be available to treat any allergic reactions.
- The clinical team will provide prescriptions for epinephrine auto-injectors for participants that experience systemic allergic reactions who do not have them. In addition, participants will receive Food Allergy Action Plan at the OFC visit if they do not have one already. The PI or designee will review the plan including symptoms of an allergic reaction and steps to take in the event of an allergic reaction, including training on how to use the epinephrine auto-injector, with the participant prior to discharge.

c. What are the benefits?

iii. To the individual

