Briefly, the DSMB will meet at study initiation, every 6 months while the study is enrolling, and at least once after the final subject is enrolled and finishes study activities. All adverse events will be compiled and reported to the DSMB in written format. Any serious adverse events deemed possibly, probably, or definitely related to study procedures will be communicated to the chair of the DSMB who will decide whether the Board needs to have an interim meeting to

discuss the event. We anticipate 4-5 scheduled DSMB meetings during the 12–24-month study period.

b. Adverse Events

Adverse Events (AEs): Any untoward medical occurrence associated with the use of an intervention in humans, whether or not considered intervention related. AEs include expected and unexpected harmful effects, and unexpected risks of an interaction or an intervention.

Serious Adverse Event (SAE): An adverse event or suspected adverse reaction is considered “serious” if, in the view of the investigator:

1. Death.
2. A life-threatening event: An AE is considered “life-threatening” if, in the view of the investigator, its occurrence places the subject at immediate risk of death. It does not include an AE that, had it occurred in a more severe form, might have caused death. **For the purposes of this study, which is expected to include anaphylaxis during the majority of these food challenges, if the anaphylaxis event is treated during the study visit and does not require escalation to Emergency Room care, this would NOT be considered an SAE.**
3. Inpatient hospitalization.
4. Persistent or significant incapacity or substantial disruption of the ability to conduct normal life functions.
5. Congenital anomaly or birth defect.
6. Important medical events that may not result in death, be life threatening, or require hospitalization may be considered serious when, based upon appropriate medical judgment, they may jeopardize the subject and may require medical or surgical intervention to prevent one of the outcomes listed above.

The investigator must report adverse events regardless of relationship to study therapy regimen or study mandated procedures.

i. Method of Identifying, Recording, Monitoring and Reporting Adverse Events

Identifying:

For this study, an adverse event will include the following associated with the oral food challenge:

All AEs occurring within 1 day of the OFC visit.

Collecting Adverse Events: Adverse events may be discovered through any of these methods:

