- GI: Nausea, abdominal pain (with change in activity level), two episodes of vomiting and/or diarrhea

Grade 3: Reaction involving one or more of the following organ systems:

- Lower respiratory: Throat tightness, wheezing, chest tightness, dyspnea, cough that respond to short acting bronchodilator treatment (including IM epinephrine) with or without supplemental oxygen
- GI: Severe abdominal pain, more than two episodes of vomiting and/or diarrhea
- Cardiovascular: Reduced BP with lightheadedness, presyncope or tachycardia

Grade 4: Life-threatening reaction involving one or more of the following organ systems with or without other symptoms listed in Grades 1 to 3:

- Lower respiratory: Throat tightness with stridor, wheezing, chest tightness, dyspnea, or cough associated with a requirement for supplemental oxygen and refractoriness to short-acting bronchodilator treatment (including IM epinephrine)¹
OR
- Respiratory compromise requiring mechanical support
- Cardiovascular: Reduced BP with associated symptoms of end-organ dysfunction (e.g., hypotonia [collapse], syncope) defined as: systolic BP of less than 90 mmHg or >30% decrease from baseline

Grade 5: Death

1. Examples of refractoriness could include continuous albuterol nebulizer or epinephrine IV infusion or more than three IM epinephrine injections

The investigator will also grade likelihood of systemic allergic reactions according to criteria set forth by the Brighton Collaboration case definition and guidelines for anaphylaxis. Please see attached supporting documents in Section 44.

Recording/Monitoring:

Throughout the study, the investigator will record adverse events and serious adverse events on the appropriate AE/SAE electronic Case Report Form (eCRF) regardless of the relationship to the OFC or study procedure. Once recorded, an AE/SAE will be followed until it resolves with or without sequelae, or the AE/SAE stabilizes, or until 1 days after the participant's OFC, whichever occurs first.

Attribution of Adverse Events Code Descriptor Relationship

RELATED CATEGORIES

1. Definitely Related
2. Probably Related
3. Possibly Related

NOT RELATED CATEGORY

4. Unlikely to be Related
5. Definitely not Related

Reporting:

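### The SAE exemption for anaphylaxis has no severity ceiling, so a CoFAR Grade 4 (life-threatening) reaction managed on site is not an SAE and triggers no individual notice to the DSMB chair

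*Combined protocol and SAP*

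**What the plan says.** Three parts of the protocol bear on this point.

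- **SAE definition, item 2** (Data & Safety Monitoring, part b). An event is life-threatening, and so serious, if in the investigator's view "its occurrence places the subject at immediate risk of death". A bold study-specific sentence in the same item makes an exception "if the anaphylaxis event is treated during the study visit and does not require escalation to Emergency Room care". Such an event, the sentence ends, "does not require escalation to Emergency Room care, this would NOT be considered an SAE". The reason given is that anaphylaxis is expected in most of the challenges.
- **CoFAR scale** (Grading of Systemic Allergic Reactions). The fourth grade opens "Grade 4: Life-threatening reaction involving one or more of the following organ systems". Its cardiovascular criterion is "Reduced BP with associated symptoms of end-organ dysfunction (e.g., hypotonia [collapse], syncope", with a blood pressure limit. Its lower respiratory criterion includes refractoriness to treatment, with the footnote "Examples of refractoriness could include continuous albuterol nebulizer or epinephrine IV infusion or more than three IM epinephrine injections".
- **DSMB reporting** (Data & Safety Monitoring, part a). "Any serious adverse events deemed possibly, probably, or definitely related to study procedures will be communicated to the chair of the DSMB", who then decides whether an interim meeting is needed. All adverse events are also compiled for the DSMB in writing. Scheduled meetings are six-monthly during enrolment. The section is a summary and refers to an attached charter for detail.

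**The concern.** The exemption depends on where the child is treated, not on how severe the reaction is. It has two conditions, treatment at the visit and no Emergency Room escalation, and neither refers to a grade. A reaction that the protocol's own scale calls life-threatening can therefore lose SAE status under the item written to give it that status.

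What would be lost is specific. The DSMB chair's decision on whether to convene between scheduled meetings is prompted by related SAEs. A Grade 4 reaction that is exempted does not prompt it. The participants are aged 6 months to 5 years, are selected because they are likely to react, and are in a trial of a new stopping rule. A Grade 4 reaction in either arm is an event on which an oversight board would normally want individual notice.

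**Working it through.** The point rests on comparing the text. The arithmetic only gives its scale.

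**Step 1: Can a Grade 4 reaction meet both conditions of the exemption?**

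| Condition | What the documents say about Grade 4 |
|---|---|
| Treated at the visit | Potential Risks foresees oral, IM or IV medication for reactions, with investigators available within 60 seconds. The risk-reduction list adds "Emergency medications, oxygen, and equipment will be available to treat any allergic reactions". |
| No Emergency Room escalation | The cardiovascular criterion is set by blood pressure and end-organ symptoms. One example of refractoriness is a count of IM injections. Neither includes transfer as part of the definition, and nothing in the adverse event section ties Grade 4 to escalation. |

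So it can. Some Grade 4 reactions, such as those needing mechanical respiratory support, would probably be escalated and would then fall outside the exemption.

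**Step 2: Does another SAE item restore the status?**

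- Item 1 (death) and item 3 (inpatient hospitalization) stand on their own, but do not reach a reaction resolved at the visit.
- Item 6 (important medical events) is discretionary: such events may be considered serious on medical judgment. The exemption is categorical and specific to this trial. Item 6 does not clearly override it.

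**Step 3: What reporting is left?**

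- The event is recorded as an adverse event, graded, and included in the written compilation for the DSMB.
- It also goes to the IRB on that body's timetable, at least yearly.
- Individual communication to the chair is lost. A reaction to the challenge food would ordinarily count as related to a study procedure, so relatedness is not the obstacle. The missing SAE label is.

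**Step 4: Scale.** Inputs from Statistical Design, Population size: 20 children per group, anaphylaxis rates of 80% (control) and 30% (intervention), 80% power, two-sided alpha 0.05, Fisher's exact test.

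- The plan's own figure reproduces. The continuity-corrected two-proportion formula gives 19 per group, 38 in total; exact Fisher power at 19 per group is 0.852; and 38 / 0.95 = 40.
- Expected anaphylaxis of any grade: 20 × 0.80 + 20 × 0.30 = 16 + 6 = 22 of 40, or 55%. This agrees with the statement that most challenges will include anaphylaxis.
- The documents give no Grade 4 proportion. Let *q* be the assumed share of anaphylaxis events that are Grade 4, the same in both arms. The chance of at least one in the trial is 1 − (1 − 0.8*q*)^20 × (1 − 0.3*q*)^20.

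| Assumed *q* | Expected Grade 4 events (22*q*) | Chance of at least one |
|---|---|---|
| 1% | 0.22 | 20% |
| 2% | 0.44 | 36% |
| 5% | 1.1 | 67% |
| 10% | 2.2 | 90% |

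These rows are illustrations. They count all Grade 4 reactions, including any that would be escalated and so remain SAEs.

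**The case against.** The strongest defence is that the exemption is deliberate and its reason is stated. Anaphylaxis is both the primary endpoint and the expected result of most challenges, so reporting every case as an SAE would bury the signal. That stands, and it supports keeping an exemption for milder reactions. It does not explain why the exemption has no ceiling.

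A second defence is that grade and seriousness are separate tests. Item 2 depends on the investigator's view of immediate risk of death, and a Grade 4 label does not by itself settle that. This also stands. But the exemption applies even where the investigator judges the risk of death to be immediate, so the conflict remains.

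Third, the DSMB charter and the IRB's reporting timetable were not available, and either may contain another trigger. This limits what can be said about oversight as a whole. It does not reconcile the two protocol sections.

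A reader might also infer more than the documents support:

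- *That all anaphylaxis treated on site is exempt, or that the worst cases are.* Absence of Emergency Room escalation is also required, and deaths and hospital admissions remain SAEs.
- *That exempted reactions are hidden from the DSMB, or reach it only every six months.* They are in the compiled reports. Six months is the meeting interval; no frequency is given for the written reports.
- *That prompt or expedited notice is lost.* No time limit is stated even for SAEs. What is lost is individual notice.
- *That the anaphylaxis expected between meetings measures the problem.* That count covers all grades. The number of Grade 4 events is unknown and could be zero.

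**Conclusion.** The concern holds in this limited form. The exemption in SAE item 2 and the Grade 4 label in the CoFAR scale contradict each other. If the protocol is followed literally, a life-threatening reaction managed on site without Emergency Room escalation, hospitalization or death is not an SAE and does not prompt the chair's decision on an interim meeting. This is a rule that gives the wrong result when applied, not a missing detail.

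The number of children affected cannot be estimated from the documents. The exemption applies to the trial's main expected harm, about 22 of 40 children at the planning rates, but only the Grade 4 part of that is at issue. The conclusion assumes that neither the charter nor the IRB timetable supplies an individual trigger for Grade 4 reactions. If one does, the practical loss shrinks, but the two sections still need to be reconciled. Sample size, power and alpha are unaffected.

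**What to change.** Put a severity ceiling on the exemption in SAE item 2. For example: *Anaphylaxis of CoFAR Grade 1, 2 or 3 that is treated at the visit without Emergency Room escalation is not reported as an SAE. Any Grade 4 reaction is an SAE wherever it is treated, and is communicated to the DSMB chair.* Grade 5 needs no mention because death is already item 1. Check the DSMB charter for consistent wording.

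The change concerns safety reporting only and leaves the treatment of reactions as it is. The exemption stays for the milder anaphylaxis that the trial expects. The cost is one amended sentence and possibly a few additional SAE reports. If every Grade 4 reaction would have been escalated anyway, the change adds no reports.

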Objectives: Primary Objective: *Define anaphylaxis rates in OFCs for peanut allergy halted by TEWL stopping rules plus standard of care clinical assessment versus control OFCs, where challenges are halted based only on clinical assessment of reaction status per standard of care.*

Secondary Objectives:

1. Define overall allergic reaction rates in peanut OFCs halted by TEWL stopping rules versus usual care.
2. Define anaphylaxis likelihood and severity via Brighton and CoFAR criteria among anaphylaxis reactions in peanut OFCs halted by TEWL stopping rules versus usual care.

Endpoints: Primary Endpoint: Anaphylaxis occurrence rate

Secondary Endpoints: Secondary endpoints will include anaphylaxis severity and overall allergic reaction rates.

Anaphylaxis likelihood will be defined by the Brighton criteria. Anaphylaxis severity will be defined via the modified CoFAR criteria (these are defined in the protocol).

Study Population: The total study population will be 40 individuals aged 6 months to 5 years, any gender, any demographic group, with a high likelihood of peanut allergy (defined in protocol). The study will take place in Michigan.

Phase: N/A

Description of Sites/Facilities This will be a single center study at the University of Michigan in Ann Arbor, MI.

[figure not shown]
Enrolling Participants:

Description of Study Intervention: This study will evaluate the use of transepidermal water loss (TEWL) continuous measurement during oral food challenge for food allergy (peanut). A stopping rule based on TEWL will be tested against usual oral food challenge care. In both cases, the standard of care will be used, where even a single symptom of an allergic reaction is used to stop oral food challenges. TEWL measures the rate of water loss from the skin in $\text{g}/\text{m}^2/\text{h}$ as a flux of water mass through an area over time.

Study Duration: 24 months

Participant Duration: Up to 9 days

Schema

Schedule of Activities

Procedures	Screening Day -7 to -1	OFC visit Visit 1, Day 1	Check-in Day 2	call,
Pre-screening questions	X			
Informed consent	X			
Confirm eligibility	X	X		
Demographics	X			
Medical history	X			
Randomization	X			
Administer study OFC		X		
Concomitant medication review	X			
Physical exam (including height and weight)		X		
Vital signs		X		
Weight		X		
Adverse event review and evaluation	X	X	X	
Complete Case Report Forms (CRFs)	X	X	X	

1. Objective

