Outcome measures. The outcome measures collected for each group in Table 2 show the hypothesized relationship for each group. If a stopping rule is implemented, that will be considered a positive challenge. We hypothesize that the intervention group will have lower anaphylaxis rates and/or severity via earlier OFC stoppage and earlier time to or more frequent treatment with non-epinephrine medications (such as antihistamines). We suspect the overall reaction rate will remain the same, but that these reactions will not devolve into anaphylaxis in the intervention group due to the above factors. Anaphylaxis will be defined according to current practice parameters ⁷², which is broadly considered to be at least two symptoms consistent with allergic reactions (cutaneous, gastrointestinal, respiratory, elevated heart rate, among others) or a decrease in blood pressure.

Post-OFC

1. Participants without evidence of an allergic reaction during the OFC will receive a follow-up phone call 1 day after the OFC to follow up on any additional symptoms or concerns.

2. Participants that had a reaction will be scheduled for a follow-up call within 1 day of the OFC to assess for additional symptoms or resolution of symptoms per the standard of care.

c. Subject Withdrawal

- i. Under what conditions will a subject be withdrawn prior to completion
- ii. If a subject withdraws prior to completion, what is the plan for the use of their data

Any subject may withdraw at any time for any reason. These reasons may include but are not limited to:

- Subject's request, no reason needed
- Adverse event – at Investigator's request. Potential examples include concern that proceeding further would impose unanticipated risk not otherwise delineated here or for any reason that continued participation could impact study integrity.

The data for any subject who withdraws prior to completion will be flagged as incomplete data in our data set. We will delete data if the subject requests this.

d. Data Retention and/or Data Destruction Plan

- i. How long will you keep subject data?
- ii. If you plan to destroy the data, how will you destroy it?

Data collected will be retained for study record keeping purposes and for future research use for up to 5 years or in accordance with our sponsor's policies. Thereafter, data will be fully de-identified fully and retained indefinitely. No data will be destroyed.

Risks & Benefits

- a. What are the risks and what will be done to monitor the risks?

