We will report any adverse events and other reportable incidences and occurrences (ORIO) to the IRB. Any adverse event or ORIO will be documented of that event including a description, subject number, date, outcome, and follow-up. Reporting of adverse events and ORIOs will follow IRBMED's reporting timetable and will occur at least yearly.

Statistical Design

Stopping rules. The anaphylaxis prediction threshold used in the study 2 trial will be data-driven based on results from our ongoing data collection study. We will perform a series of logistic regression models testing the predictive value of various levels of absolute increases in TEWL, thresholds of TEWL and their combinations. These will be tested against time to first symptom, time to formal anaphylaxis diagnosis, time to first medication use, and time to epinephrine use. To avoid overfitting, these analyses will use a 2:1 derivation: validation random split. Corrections will include baseline TEWL value and variance. A minimum sustained timespan meeting the threshold (such as 30-60 seconds) may be needed to minimize the effects of noise in the measurement.

Endpoints. The primary endpoint will be anaphylaxis rate among the intervention group versus the control group and will be reported with a 95% confidence interval. Secondary endpoints will include anaphylaxis severity and overall reaction rates. Exploratory endpoints may include but are not limited to time to first treatment, time to first symptom, epinephrine use, any medication use, and time to meeting a stopping rule (regardless of whether it was implemented); all will be reported with 95% confidence intervals. Exact p-values will be calculated using Fischer's test.

Descriptive analyses. Descriptive analyses will be reported. Continuous baseline measures will be reported using either mean (or geometric mean) with 95% confidence interval or median with first and third quartiles, as appropriate. Categorical baseline and demographic characteristics and study disposition will be reported as frequencies and proportions.

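### Follow-up of every adverse event, serious ones included, ends one day after the challenge, so an event neither resolved nor stable by then has no outcome in the protocol record

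*Combined protocol and SAP*

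**What the plan says.** Data & Safety Monitoring, section b (Adverse Events), uses the same one-day limit for two purposes.

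- **Onset.** Under Identifying, the events collected are "All AEs occurring within 1 day of the OFC visit".
- **End of follow-up.** Under Recording/Monitoring, resolution is the first of three end points for a recorded event, and the sentence then adds the other two: "or the AE/SAE stabilizes, or until 1 days after the participant's OFC, whichever occurs first". AEs and SAEs share this one sentence.

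The visit plan agrees. In the Post-OFC section, "Participants that had a reaction will be scheduled for a follow-up call within 1 day of the OFC"; children without a reaction are also called one day after the challenge. The Schedule of Activities has no contact after the Day 2 check-in.

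Two other places need information on how an event ended. The Reporting paragraph states: "Any adverse event or ORIO will be documented of that event including a description, subject number, date, outcome, and follow-up". The section on the data safety and monitoring board (DSMB) sends SAEs judged at least possibly related to the study procedures to the chair, who decides whether an interim meeting is needed.

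**The concern.** A one-day window for onset is a reasonable choice for a single challenge with immediate reactions. Using the same day to stop following an event already known to be open is a different matter. Because the rule takes the earliest of three conditions, an event still evolving on Day 2 is dropped by the calendar and not by its clinical course.

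The events exposed to this are the least common and the most serious. The SAE list includes inpatient hospitalisation, which can run past the next day, and persistent incapacity, which can hardly be judged in one day. Anaphylaxis treated at the visit without escalation to the emergency room is excluded from the SAE definition. An anaphylaxis SAE will therefore generally be an escalated one, and its course is the least certain to be settled by Day 2.

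What is at stake is the completeness of the safety record, in children aged 6 months to 5 years who are enrolled because a reaction is likely, and the information on which the DSMB chair acts.

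**Working it through.** **1. Is there any scheduled contact after Day 2?** The Schedule of Activities gives "Screening Day -7 to -1", then "OFC visit Visit 1, Day 1", then the check-in on Day 2. There is no Day 0.

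Days = 7 (Day -7 to Day -1) + 1 (Day 1) + 1 (Day 2) = 9.

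This reproduces the Synopsis, "Participant Duration: Up to 9 days". The stated duration leaves no room for a later contact.

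**2. How much follow-up does the rule allow?** For an event starting *t* days after the OFC (0 ≤ *t* ≤ 1, the onset window):

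maximum follow-up = 1 − *t* days.

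That is 1 day for a reaction at the challenge (*t* = 0) and 0 days for an event that starts at the end of the window (*t* = 1).

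**3. Which events lose information?** Take the state of the event at the Day 2 call:

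| State at Day 2 | Present rule | Rule proposed under the fix |
|---|---|---|
| Resolved | Closed, outcome known | Same |
| Stable, symptoms still present | Closed by stabilisation | Same |
| Neither resolved nor stable | Closed by the one-day limit, outcome unknown | Followed until resolved or stable |

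Only the third row changes.

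**4. Does other text lift the limit?**

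- Post-OFC: the call assesses whether symptoms have resolved, but nothing says what follows if they have not.
- Collecting Adverse Events: families may phone in events. That is a way of discovering events, not follow-up of a known one.
- DSMB: related SAEs are passed to the chair, but follow-up is not extended.
- Reporting: outcome and follow-up are required, but no time point is given.

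None of these sets a later end date or an exception for SAEs.

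**5. Does it touch the trial's comparisons?** Table 2 compares the arms on Brighton level, reaction rate, CoFAR grade and Brighton score. The exploratory list covers symptoms, medication use and times to first symptom, first treatment or stopping rule. None uses the duration or later outcome of an AE. The planned 19 per group (80% versus 30%) does not depend on the follow-up rule.

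**The case against.** The strongest reply is that little is lost in practice. The visit already includes 1–2 hours of monitoring or treating reactions, and the protocol expects a need for urgent care after the visit to be rare. The Reporting paragraph can be read as a separate duty to document follow-up, and an outcome may be entered as ongoing, so the two texts can coexist. The DSMB charter and the IRB reporting timetable, neither of which is among the documents reviewed, may ask for later outcomes. Nothing forbids staff from recording more than the rule requires. Most of this stands. It limits how often the gap matters and makes the two texts a tension, not a strict contradiction. It does not remove the ceiling, which staff would apply as written.

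Three stronger readings are tempting and are not supported:

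- *The cut-off hides the events that would distinguish the arms.* No planned comparison uses AE duration or later outcome. CoFAR grades 1–4 rest on symptoms and response to treatment, not on time to recovery. A grade could be understated only if a reaction worsened after Day 2, and the documents give no ground to expect that.
- *About 22 of 40 children are affected.* The planned rates give 20 × 0.80 + 20 × 0.30 = 22 expected anaphylaxis events. That counts the events that occur, not those still open at Day 2.
- *Any child with symptoms at the Day 2 call is lost.* A child whose symptoms are stable is closed by stabilisation, under the present rule and under the amended one.

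**Conclusion.** The point holds as a gap in safety data collection. As written, no AE or SAE is followed beyond one day after the OFC, and an event neither resolved nor stable at that time leaves protocol follow-up without a known outcome. The number of such events cannot be derived from the documents. That they are probably few is an assumption, resting on same-day treatment of most reactions; no resolution times are given. The primary endpoint, sample size and power are unaffected. The conclusion concerns the research record and says nothing about clinical care, which presumably continues. It holds for the text supplied and could be softened by the DSMB charter or the IRB timetable. The change is worth making because it is cheap and the affected events, however rare, are those on which a safety board most needs the full course.

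**What to change.** Keep the one-day window for onset. Replace the follow-up sentence in Recording/Monitoring with wording such as:

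> SAEs, and any AE neither resolved nor stable at the Day 2 call, are followed for data collection until resolution or stabilisation, even when this is more than 1 day after the OFC. All other AEs are followed until resolution, stabilisation or 1 day after the OFC, whichever is earliest.

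Add a cross-reference from Reporting, so that the outcome and follow-up required there are those collected under this rule. Qualify the 9-day participant duration in the Synopsis to allow for these cases, and check that the DSMB charter agrees.

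The cost is the wording change, an occasional extra phone call or chart check, and a longer participation for the few children concerned. It changes no treatment, endpoint or analysis.
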